5.4. Screen Failures

A screen failure occurs when a participant who consents to participate in the clinical study is not subsequently enrolled in the study. A minimal set of screen failure information is required to ensure transparent reporting of screen failure participants to meet the Consolidated Standards of Reporting Trials (CONSORT) publishing requirements and to respond to queries from regulatory authorities. Minimal information includes demography, screen failure details, eligibility criteria, and any SAE.

Individuals who do not meet the criteria for participation in this study (screen failure) may be rescreened 1 time.

A possible reason for rescreening may be a status change such that the eligibility criterion that caused the participant to screen fail would not cause the participant to screen fail again.

If an individual is rescreened, a new participant number is assigned, and the individual must sign a new ICF.

5.5. Criteria for Temporarily Delaying Enrollment of a Participant

This section is not applicable for this study. All entry criteria must be met within the specified visit intervals in the SoA.

6. Study Intervention(s) and Concomitant Therapy

Study intervention is defined as any investigational intervention(s), marketed product(s), placebo, or medical device(s) intended to be administered to/used by a study participant according to the study protocol.

6.1. Study Intervention(s) Administered

Study intervention will be administered at the study sites, at visits summarized in the SoA.

This table provides information for the interventions used in this clinical study.

Study intervention dosing information

Each dose of study intervention is planned to be CC The sponsor will provide detailed instructions for study intervention administration in a separate document.

After dosing, the investigator should monitor all participants for 1 hour or longer according to investigator practice or local standard of care.

[figure not shown]

Packaging and labeling

Study interventions will be supplied by the sponsor or its designee in accordance with current Good Manufacturing Practice. Study interventions will be labeled as appropriate for country requirements.

6.1.1. Rescue Medicine

Guidance for starting rescue therapy

6.2. Preparation, Handling, Storage, and Accountability

The investigator or designee must confirm appropriate storage conditions have been maintained during transit for all study intervention received and any discrepancies are reported and resolved before use of the study intervention.

Only participants enrolled in the study may receive study intervention. Only authorized study personnel may supply, prepare, or administer study intervention. All study intervention must be stored in a secure, environmentally controlled, and monitored (manual or automated) area in accordance with the labeled storage conditions with access limited to the investigator and authorized study personnel.

The investigator or authorized study personnel are responsible for study intervention accountability, reconciliation, and record maintenance (that is, receipt, reconciliation, and final disposition records).

Further guidance and information for the final disposition of unused study interventions are provided in the Pharmacy Manual.

6.3. Measures to Minimize Bias: Randomization and Blinding

Randomization

Blinding

This is a double-blind study. Blinding will be maintained throughout the conduct of the study, as described in the separate Blinding and Unblinding Plan.

Investigators will remain blinded to each participant's assigned study intervention within each dose group, throughout the course of the study.

Emergency unblinding

The IWRS will be programmed with blind-breaking instructions. In case of an emergency, the investigator has the sole responsibility for determining if unblinding of a participants' intervention assignment is warranted. Participant safety must always be the first consideration in making such a determination.

If a participant's intervention assignment is unblinded, the sponsor must be notified immediately within 24 hours of this occurrence. The date and reason that the blind was broken must be recorded.

Discontinuation from the study in case of unblinding

If an investigator, site personnel performing assessments, or participant is unblinded, the participant must be discontinued from the study. In cases where there are ethical reasons to have the participant remain in the study, the investigator must obtain specific approval from the sponsor for the participant to continue in the study.

6.4. Study Intervention Compliance

6.5. Dose Modification

This protocol does not allow dose adjustments.

6.6. Continued Access to Study Intervention after the End of the Study

Study intervention will not be available to participants after completion of the study.

If an open-label extension study is enrolling at the time the participant completes Visit 18 (Week 60), they will be given the opportunity to enroll in that study.

6.7. Treatment of Overdose

The sponsor does not recommend specific treatment for an overdose.

In the event of an overdose, the investigator should

- contact the medical monitor immediately
- evaluate the participant to determine, in consultation with the medical monitor, whether study intervention should be interrupted
- closely monitor the participant for any AE/SAE and laboratory abnormalities

6.8. Concomitant Therapy

General considerations

Concomitant therapy data collection

For therapy that the participant is receiving at the time of enrollment or receives during the study, whether prescription or over-the-counter, authorized study personnel should collect

- the name of medication, vaccine or therapy
- the reason for use
- route of administration, and
- dates of administration, including start and end dates.

For RA background therapy and rescue therapy, study personnel should collect additional dosing information, including dose and frequency.

The medical monitor should be contacted if there are any questions regarding concomitant or prior therapy.

7. Discontinuation of Study Intervention and Participant Discontinuation/Withdrawal

This section outlines

- Permanent discontinuation of study intervention
- Temporary interruption of study intervention
- Discontinuation from the study, and
- Participants lost to follow-up.

Discontinuation of specific sites or of the study as a whole are handled as part of Section 10.1, Appendix 1.

7.1. Discontinuation of Study Intervention

Permanent discontinuation of study intervention

When necessary, a participant may be permanently discontinued from study intervention. If so, the participant will be encouraged to remain in the study and follow procedures for all remaining study visits, as shown in the SoA.

A participant should be permanently discontinued from study intervention if the participant

- requests to discontinue the study intervention
- becomes pregnant during the study
- is diagnosed with an active or untreated malignancy, except for successfully treated basal or squamous cell carcinoma
- is diagnosed with HIV infection
- is diagnosed with active TB
- is diagnosed with LTBI and are not a candidate for treatment as described in Section 8.2.8
- tests positive for HBV DNA or HCV RNA (see Sections 8.2.9 and 8.2.10 for details)
- answered "yes" to Question 4 or Question 5 on the "Suicidal Ideation" portion of the C-SSRS
- answered "yes" to any of the suicide-related behaviors on the Suicidal Behavior portion of the C-SSRS
 - A psychiatrist or appropriately trained professional may assist in the decision to discontinue the participant.
- has a systemic hypersensitivity reaction related to study intervention administration,
 or
- in the opinion of the investigator, the participant should permanently discontinue the study intervention for safety reasons.

Additional guidance

Escape criteria

A participant not achieving **CC**

or example, if a participant meets rescue criteria at Week 16 and does not achieve a 20% improvement from baseline in both TJC and SJC at Weeks 20 and 24, then they should be permanently discontinued from study intervention. Participants may continue in the study and receive additional standard of care therapies at the investigator's discretion.

Systemic hypersensitivity reactions

If the investigator determines that a systemic hypersensitivity reaction has occurred related to study intervention administration, the sponsor's designated medical monitor should be notified.

If the investigator is uncertain about whether a systemic hypersensitivity reaction has occurred and whether discontinuation of study intervention is warranted, the investigator may consult the sponsor.

HBV DNA

Prior to discontinuation of any immunomodulatory or immunosuppressive therapy, including study intervention, the participant should be referred to, evaluated, and managed by a physician with expertise in evaluation and management of viral hepatitis.

The timing of discontinuation from study intervention relative to the initiation of any antiviral treatment for hepatitis should be based on the recommendation of the consulting physician with expertise in hepatology, in conjunction with the investigator, and aligned with medical guidelines and standard of care.

7.1.1. Liver Chemistry Stopping Criteria

Interrupting study intervention based on elevated liver tests

The study intervention should be **interrupted** and close hepatic monitoring initiated (see Section 8.2.7), if 1 or more of the conditions in this table occur.

Elevation	Exception
ALT or AST >8x ULN	
ALT or AST >5x ULN for more than 2 weeks	
ALT or AST >3x ULN and either TBL >2x ULN or INR >1.5	For participants with Gilbert's syndrome: If baseline direct bilirubin is >0.5 mg/dL, then doubling of direct bilirubin should be used for drug interruption decisions rather than TBL>2x ULN.
ALT or AST >3x ULN with the appearance of fatigue, nausea, vomiting, right upper quadrant pain or tenderness, fever, rash, and/or eosinophilia (>5%)	
ALP >3x ULN, when the source of increased ALP is the liver	
ALP >2.5x ULN and TBL > 2x ULN	For participants with Gilbert's syndrome: If baseline direct bilirubin is >0.5 mg/dL then doubling of direct bilirubin should be used for drug interruption decisions rather than TBL>2x ULN.

ALP >2.5x ULN with the appearance of fatigue, nausea, vomiting, right upper quadrant pain or tenderness, fever, rash,	
and/or eosinophilia (>5%)	
Source: FDA 2009 and other consensus guidelines, with minor modifications.	

Resuming study intervention after elevated liver tests

Resumption of the study intervention can be considered only in consultation with the Lilly-designated medical monitor and only if the liver test results return to baseline and if a self-limited, non-drug etiology is identified. Otherwise, the study intervention should be permanently discontinued.

7.1.2. QTc Stopping Criteria

If a clinically significant finding is identified, including, but not limited to changes from baseline after enrollment, the investigator or qualified designee will determine if the participant can continue in the study and if any change in participant management is needed. This review of the ECG printed at the time of collection must be documented. Any new clinically relevant finding should be reported as an AE.

7.1.3. Temporary Discontinuation of Study Intervention

Infection-related criteria for temporary discontinuation of study intervention

This table describes the required criteria for temporarily discontinuing study intervention and the next steps the site staff should follow.

If a participant develops	Then follow this guidance
serious or opportunistic infections, as defined in the	Withhold study intervention until resolution of all
exclusion criteria (Section 5.2)	acute clinical signs and symptoms, and completion of
	all appropriate anti-infective treatment.
	The investigator should consult with the sponsor-
	designated medical monitor to determine when it is
	appropriate to restart study intervention.
any acute infection or illness	At the discretion of the investigator and sponsor or its
	designee, withhold intervention until resolution of all
	acute clinical signs and symptoms, and completion of
	all appropriate anti-infective treatment.
positive HBV DNA results	Contact the sponsor-designated medical monitor.
or	Repeat HBV DNA testing as soon as possible.
results detecting HBV DNA, but the HBV DNA is	If HBV DNA is confirmed as positive, then
below the level of quantification	permanently discontinue intervention.
LTBI and the participant is a candidate for LTBI	Withhold study intervention for at least the first 4
treatment	weeks of LTBI treatment.
	If there is no evidence of hepatotoxicity
	(ALT/AST must remain ≤2 times ULN) or other
	treatment intolerance after receiving at least 4
	weeks of appropriate LTBI therapy, per WHO or
	CDC guidelines, then restart study intervention.
	The participant must complete appropriate LTBI
	therapy before restarting study intervention.

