5.2. Exclusion Criteria

- 20. Have had any surgical procedure, within 12 weeks prior to screening, or any planned surgical procedure scheduled to occur during the study, with the exception of minor surgery requiring local or no anesthesia and without any complications or sequelae.
- 21. Have had any of the following types of infections within 3 months of screening or develops any of these infections before the randomization visit
 - Serious requires hospitalization or IV or equivalent oral antibiotic treatment
 - Opportunistic as defined in Section 10.7
 - Chronic duration of symptoms, signs, or treatment of 6 weeks or longer
 - Recurring including, but not limited to, herpes simplex, herpes zoster, recurring cellulitis, or chronic osteomyelitis
 - Note: Herpes zoster is considered active and ongoing until all vesicles are dry and crusted over
 - Exception: If the investigator determines that a participant with recurrent nonserious infections such as cellulitis and uncomplicated orolabial or genital herpes, is not at an increased risk of complications.

[figure not shown]
22. Have any of these infections

- HIV infection
- current infection with HBV, for example, positive for hepatitis B surface antigen (HBsAg) or polymerase chain reaction (PCR) positive for HBV DNA
- current infection with HCV, for example, positive for HCV RNA, or
- active TB.
- 23. Have or had LTBI that has not been treated with a complete course of appropriate therapy as defined by the WHO or the United States CDC, unless such treatment is underway, as per Section 8.2.8.
- 24. Have a current or recent acute active infection, or fever of 100.5°F (38°C) or above, at screening or baseline. For at least 30 days prior to screening, participants must have no symptoms or signs of confirmed or suspected infection and must have completed any appropriate anti-infective treatment.
- 25. Are women who are currently pregnant or breastfeeding, or who intend to become pregnant or to breastfeed at any time during the study or within 20 weeks after receiving the last dose of study intervention.

[figure not shown]
Prior/concomitant therapy

[figure not shown]
26. Have failed more than CCI

27. Are currently receiving or have received any of these therapies within 28 days CC

28. Have received these treatments CCI or plan on receiving any of these biologic immunosuppressive treatments during the study

[figure not shown]

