8.2.8. Tuberculosis Testing and Monitoring

Tuberculosis testing at screening Visit 1

Medical history will determine the lifetime risk factors for TB infection, for TB progression, and for symptoms or signs of active TB.

A physical examination will determine symptoms of active TB, including measurement of body temperature and assessment of peripheral lymph nodes.

A chest x-ray will be interpreted and reported by a radiologist or pulmonologist, as specified in the SoA (Section 1.3). Participants do not need to have a chest x-ray at screening if results from a chest x-ray within 3 months prior to the study are available.

All participants with no history of LTBI or active TB, and no history of positive Mantoux tuberculin skin test (TST) using purified protein derivative (PPD) or positive *Mycobacterium tuberculosis* interferon gamma release assay (IGRA), must have either a PPD, TST or IGRA for *M. tuberculosis*.

PPD TST

An induration of 5 or more millimeters is considered positive in persons

- with HIV-infection
- with a recent contact with a person with TB disease
- with fibrotic changes on chest radiograph consistent with prior TB
- with organ transplants, or
- who are immunosuppressed for other reasons, for example, taking the equivalent of >15 mg/day of prednisone for 1 month or longer, or taking tumor necrosis factor -α antagonists.

An induration of 10 or more millimeters is considered positive in all other potential study participants.

Two-step testing, repeating TST from 1 to 3 weeks after the first TST, is recommended for certain participant groups, including persons

- receiving immunosuppressant treatment
- with a history of temporally remote increased risk of TB infection, or
- for whom the first test is negative, as per local public health or professional medical society recommendations.

IGRA for M. tuberculosis

Ensure that specimen handling, transport, timing, and laboratory procedures meet all requirements per package insert.

Diagnosed LTBI

Participants diagnosed with LTBI are excluded (Section 5.2) unless they are candidates for LTBI treatment, are treated for LTBI, and the following criteria are met:

[figure not shown]
- After receiving at least 4 weeks of LTBI therapy, per the WHO or the United States CDC guidelines, there is no evidence of hepatotoxicity, defined as ALT/AST ≤2 times ULN, or other treatment intolerance.
- The participant completes appropriate LTBI therapy.

Monitoring during the study

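### Protocol 7.1.3 gives two different earliest restart times for study drug after a latent TB diagnosis and does not say which governs

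*Protocol*

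**What the plan says.** Protocol 7.1.3 has a table of infection-related criteria for temporarily stopping study drug, which the text presents as required. The row for LTBI in a participant who can be treated makes three statements:

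1. "Withhold study intervention for at least the first 4" weeks of LTBI treatment.
2. If there is no hepatotoxicity (ALT/AST staying at or below 2 times ULN) or other "treatment intolerance after receiving at least 4" weeks of therapy, restart. The sentence closes "CDC guidelines, then restart study intervention".
3. A final sentence begins "The participant must complete appropriate LTBI" and ends "therapy before restarting study intervention".

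Three other places deal with LTBI:

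- **Exclusion criterion 23 (Section 5.2)** bars people whose LTBI has not been fully treated, "unless such treatment is underway, as per Section 8.2.8".
- **Section 8.2.8**, under testing at the screening visit, sets two conditions. One is a check after at least 4 weeks of therapy that "there is no evidence of hepatotoxicity, defined as ALT/AST ≤2 times ULN, or other treatment intolerance". The other is that therapy is completed, with nothing on whether completion must come before dosing.
- **Section 7.1** requires permanent discontinuation for LTBI only when the participant cannot be treated for it.

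**The concern.** Consider a participant diagnosed with LTBI on study who reaches week 4 of a longer course with acceptable liver tests and no intolerance. Statement 2 directs a restart and statement 3 forbids it. The row names no one to decide. By contrast, the row for serious or opportunistic infections in the same table sends the restart decision to the medical monitor.

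Two things are at stake. The first is consistent conduct: two sites could treat identical participants differently and each could cite the protocol. The second is safety: the choice settles whether study drug is given alongside LTBI therapy, during which the protocol itself asks for a hepatotoxicity check. Exposure to study drug would also vary with the site's reading.

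**Working it through.** The plan gives no figure to reproduce, so the check is mainly a comparison of texts, with one simple calculation for size.

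**Can both sentences be obeyed?** Let L be the length of the LTBI course in weeks, starting when study drug is withheld, with L at least 4.

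- Statements 1 and 2 give an earliest restart at week 4.
- Statement 3 gives an earliest restart at week L.
- The two agree only when L = 4. For L above 4, a site restarting between week 4 and week L follows statement 2 and breaks statement 3.

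**Does another section settle it?**

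- Exclusion 23 accepts LTBI treatment that is still in progress, but it concerns entry, not restart.
- Section 8.2.8 lists the 4-week check and completion of therapy without ordering completion and dosing. It also concerns entry.
- Section 7.1 covers only participants who cannot be treated.

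None of these states which sentence in 7.1.3 governs.

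**Is it an artefact of redaction or table extraction?** No. Both sentences are complete, sit in the same cell, and are current text, not part of the amendment history.

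**Size of the gap.** Gap = L − 4 weeks. Divide by 4 for four-weekly (Q4W) dosing intervals. The documents refer to WHO and CDC guidelines for the course but give no length, so the values of L below are assumed.

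| Assumed L (weeks) | Gap L − 4 (weeks) | Q4W intervals, gap / 4 |
|---|---|---|
| 4 | 0 | 0 |
| 12 | 8 | 2 |
| 24 | 20 | 5 |
| 36 | 32 | 8 |

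For scale, the treatment period in SAP 1.2 is 60 weeks. Some participants may move to 12-weekly (Q12W) dosing at Week 24. For them the longest gap shown is 32 / 12 = 2.7 dosing intervals, so the Q4W count is the upper end.

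**Hepatotoxicity wording.** In 7.1.3, ALT/AST at or below 2 times ULN is the condition for no hepatotoxicity. In 8.2.8 the words that follow the comma could attach to hepatotoxicity alone, which would reverse the meaning, or to the whole phrase about its absence, which agrees with 7.1.3. Inclusion criterion 8 requires ALT and AST at or below 2 times ULN at entry, so only the second reading makes sense.

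**The case against.** The strongest reply is that the row can be followed. The 4 weeks is stated as a minimum in both places. A site that confirms tolerance at week 4 or later and restarts only when the course ends breaks neither sentence. This stands, and a reader who infers that compliance is impossible goes too far. It does not remove the problem: on that reading the restart instruction tied to 4 weeks has no function, and nothing tells a site that this is the intended reading.

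Three further inferences are tempting and are not supported:

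- **That a long hold makes the participant an intercurrent event.** SAP 1.1 defines the event as early discontinuation from the study or study intervention, and the SAP version 3 history clarifies it as permanent discontinuation. SAP 4.6.2 summarises temporary interruptions due to adverse events separately. No text turns a longer temporary hold into a discontinuation. Exposure could change; estimand status is not shown to change.
- **That 8.2.8 and 7.1.3 contradict each other on hepatotoxicity.** The 8.2.8 wording is loose, but its natural reading agrees with 7.1.3. This is editorial.
- **That the same rule must appear in both sections.** Section 8.2.8 qualifies eligibility at screening and 7.1.3 governs restart after an on-study diagnosis. Requiring identical rules would itself be a clinical decision.

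It is also fair to say that the gap shrinks to nothing for a 4-week course and that few participants are likely to be affected.

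**Conclusion.** The point holds as an internal inconsistency in a safety rule. The LTBI row of Protocol 7.1.3 gives two earliest restart times that differ for any course longer than 4 weeks, and no other section resolves them. The difference is 0 to 32 weeks, or 0 to 8 Q4W intervals, and depends entirely on the assumed course length of 4 to 36 weeks.

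That few participants are affected is a judgement, since the documents give no expected number. No material effect on the Week 12 ACR20 analysis is claimed. Confidence is high that the two sentences conflict as written. The documents do not show which was intended.

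**What to change.** The sponsor's clinicians should reconcile the two sentences in the LTBI row of Protocol 7.1.3 so that a site can tell whether restart during LTBI therapy is allowed. They should then check the result for consistency with Section 8.2.8 and exclusion criterion 23. This review takes no position on which rule is right or whether entry and restart should follow the same one.

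As an editorial change, 8.2.8 should be reworded so that ALT/AST at or below 2 times ULN plainly describes the absence of hepatotoxicity, as in 7.1.3.

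The cost is a protocol clarification and a letter to sites. If dosing has already ended, the sponsor can record which restart rule was applied to any affected participant and correct the text before it is reused.
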